6.3 LOST TO FOLLOW-UP

A subject will be considered lost to follow-up if he or she fails to return for 2 scheduled visits and is unable to be contacted by the study site staff.

The following actions must be taken if a subject fails to be available for a required study visit:

- The site will attempt to contact the subject and reschedule the missed visit and counsel
 the subject on the importance of maintaining the assigned visit schedule and ascertain if
 the subject wishes to and/or should continue in the study.
- Before a subject is deemed lost to follow-up, the investigator or designee will make
 every effort to regain contact with the subject (where possible, 3 telephone calls and, if
 necessary, a letter to the subject's last known mailing address or local equivalent
 methods). These contact attempts should be documented in the subject's study file.
- Should the subject continue to be unreachable, he or she will be considered to have withdrawn from the study with a primary reason of lost to follow-up.

7 STUDY ASSESSMENTS AND PROCEDURES

7.1 STUDY ASSESSMENTS

The main outcome is minutes per week of moderate- to vigorous-intensity physical activity. The 7-day PAR interview is administered by trained research staff, who will contact participants by telephone and ask about the amount, intensity, and types of physical activities over the past 7 days.

ActiGraph GT3X accelerometers are worn continuously for 7 days during waking (on the nondominant hip) and sleeping (on the nondominant wrist) hours at baseline and at 6, 12, and 18 months. This device measures movement, intensity of physical activity, and sleep efficiency, latency, and number of awakenings.

The secondary outcomes include physical performance and anthropometrics. Physical performance is assessed with the Two Minute Step Test, in which participants step in place as fast as possible for 2 minutes while lifting the knees to a premeasured height midway between the upper tips of their patella and iliac crest when standing. A score is calculated based on the number of times the right knee meets the marked height, which can be used to estimate the current level of physical function and predict future physical independence. Anthropometric measurements include height, weight, and waist circumference. Height will be measured without shoes and in light clothing with a digital scale (Healthometer, model no: 349KLX) that is zeroed before each measurement. Waist circumference will be measured with a Gulick II tension-controlled tape measure (County Technology, Gary Mills). The tape is positioned around the natural waist, just above the iliac crest. The measurement is recorded to the nearest 0.1 cm upon exhalation.

Psychosocial factors will also be assessed at baseline and at 6, 12, and 18 months using Patient-Reported Outcome Measurement Information System scales for anxiety, depression, fatigue, and sleep disturbance with previously demonstrated validity and reliability.

Social Cognitive Theory measures will be assessed in person at the 4 assessment visits and by mail at 3 months (for mediation analyses). The measures include the 10-item self-regulation scale (α =.78), 13-item social support for exercise scale (α =.61-.9), 9-item outcome expectations scale (α =.89), 18-item physical activity enjoyment scale with high internal consistency and test-retest reliability, 10-item walking self-efficacy scale (α =.82), and the 12-item exercise confidence scale (α =.92).

Secondary measures at baseline, 6 months, and 12 months were included in the cost-effectiveness analyses. We will use a health care utilization survey that captures information on physician and emergency room visits and hospitalizations; the EuroQol-5 Dimension, which estimates utility weights to estimate quality-adjusted life years (QALYs); and a set of questions to measure time spent and expenses related to participation and time devoted to physical activity.

An 18-item measure adapted from similar past studies will assess participant satisfaction with the DIAL intervention and request suggestions for program improvement at 12 and 18 months. Finally, a similar survey will be administered at 18 months to the rural county coordinators to

examine stakeholders' perspectives on acceptability, barriers to and facilitators of implementation, and sustainability of the DIAL intervention in the Deep South.

The research staff will complete the three components of the Rural Active Living Assessment (RALA) for each county at baseline. This assessment consists of the street segment assessment to evaluate factors such as walkability, safety features, and terrain of individual, specific street segments; the town-wide assessment that examines community characteristics such as population, total area, and the presence of recreation activities; and finally, the program and policy assessment, which identifies community programs and policies that support physical activity.

7.2 ADVERSE EVENTS AND SERIOUS ADVERSE EVENTS

7.2.1 DEFINITION OF ADVERSE EVENTS (AE)

Adverse event means any untoward medical occurrence associated with the use of an intervention in humans, whether or not considered intervention-related (21 CFR 312.32 (a)).

7.2.2 DEFINITION OF SERIOUS ADVERSE EVENTS (SAE)

An adverse event (AE) is considered "serious" if, in the view of either the investigator or sponsor, it results in any of the following outcomes:

- Death
- A life-threatening adverse event (of note, the term "life-threatening" refers to an event in which the subject was at risk of death at the time of the event, rather than to an event which hypothetically might have caused death if it were more severe)
- inpatient hospitalization or prolongation of existing hospitalization
- a persistent or significant incapacity or substantial disruption of the ability to conduct normal life functions
- or a congenital anomaly/birth defect.

Important medical events that may not result in death, be life-threatening, or require hospitalization may be considered serious when, based upon appropriate medical judgment, they may jeopardize the subject and may require medical or surgical intervention to prevent one of the outcomes listed in this definition. Examples of such medical events include allergic bronchospasm requiring intensive treatment in an emergency room or at home, blood dyscrasias or convulsions that do not result in inpatient hospitalization, or the development of drug dependency or drug abuse.

7.2.3 CLASSIFICATION OF AN ADVERSE EVENT

7.2.3.1 SEVERITY OF EVENT

For adverse events (AEs), the following guidelines will be used to describe severity:

- **Mild** Events require minimal or no treatment and do not interfere with the subject's daily activities.
- **Moderate** Events result in a low level of inconvenience or concern with the therapeutic measures. Moderate events may cause some interference with functioning.
- **Severe** Events interrupt a subject's usual daily activity and may require systemic drug therapy or other treatment. Severe events are usually potentially life-threatening or incapacitating. Of note, the term "severe" does not necessarily equate to "serious."

7.2.3.2 RELATIONSHIP TO STUDY INTERVENTION

All adverse events (AEs) must have their relationship to study intervention assessed by the clinician who examines and evaluates the subject based on temporal relationship and his/her clinical judgment. The degree of certainty about causality will be graded using the categories below. In a clinical trial, the study product must always be suspect.

- Related The AE is known to occur with the study intervention, there is a reasonable
 possibility that the study intervention caused the AE, or there is a temporal relationship
 between the study intervention and event. Reasonable possibility means that there is
 evidence to suggest a causal relationship between the study intervention and the AE.
- Not Related There is not a reasonable possibility that the administration of the study intervention caused the event, there is no temporal relationship between the study intervention and event onset, or an alternate etiology has been established.

7.2.3.3 EXPECTEDNESS

The Principal Investigator will be responsible for determining whether an adverse event (AE) is expected or unexpected. An AE will be considered unexpected if the nature, severity, or frequency of the event is not consistent with the risk information previously described for the study intervention.

7.2.4 TIME PERIOD AND FREQUENCY FOR EVENT ASSESSMENT AND FOLLOW-UP

The occurrence of an adverse event (AE) or serious adverse event (SAE) may come to the attention of study personnel during study visits and interviews of a study subject presenting for medical care, or upon review by a study monitor.

All AEs including local and systemic reactions not meeting the criteria for SAEs will be captured on the appropriate case report form (CRF). Information to be collected includes event description, time of onset, clinician's assessment of severity, relationship to study (assessed only by those with the training and authority to make a diagnosis), and time of resolution/stabilization of the event. All AEs occurring while on study must be documented appropriately regardless of relationship. All AEs will be followed to adequate resolution.

Any medical condition that is present at the time that the subject is screened will be considered as baseline and not reported as an AE. However, if the study subject's condition deteriorates at any time during the study, it will be recorded as an AE.

Changes in the severity of an AE will be documented to allow an assessment of the duration of the event at each level of severity to be performed. AEs characterized as intermittent require documentation of onset and duration of each episode.

The Study Coordinator will record all reportable events with start dates occurring any time after informed consent is obtained until 7 (for non-serious AEs) or 30 days (for SAEs) after the last day of study participation. At each study visit, the Study Coordinator will inquire about the occurrence of AE/SAEs since the last visit. Events will be followed for outcome information until resolution or stabilization.

7.2.5 ADVERSE AND SERIOUS ADVERSE EVENT REPORTING

All serious adverse events must be reported to the IRB according to regulatory requirements. The Principal Investigator will immediately report to the sponsor any serious adverse event, whether or not considered study intervention related, including those listed in the protocol or package insert and must include an assessment of whether there is a reasonable possibility that the study intervention caused the event. Study endpoints that are serious adverse events (e.g., all-cause mortality) must be reported in accordance with the protocol unless there is evidence suggesting a causal relationship between the study intervention and the event. In that case, the investigator must immediately report the event to the sponsor.

All serious adverse events (SAEs) will be followed until satisfactory resolution or until the Principal Investigator deems the event to be chronic or the subject is stable. Other supporting documentation of the event may be requested and should be provided as soon as possible.

7.3 UNANTICIPATED PROBLEMS

7.3.1 DEFINITION OF UNANTICIPATED PROBLEMS (UP)

The Office for Human Research Protections (OHRP) considers unanticipated problems involving risks to subjects or others to include, in general, any incident, experience, or outcome that meets **all** of the following criteria:

- Unexpected in terms of nature, severity, or frequency given (a) the research procedures that are described in the protocol-related documents, such as the Institutional Review Board (IRB)-approved research protocol and informed consent document; and (b) the characteristics of the subject population being studied;
- Related or possibly related to participation in the research ("possibly related" means there is a reasonable possibility that the incident, experience, or outcome may have been caused by the procedures involved in the research); and
- Suggests that the research places subjects or others at a greater risk of harm (including physical, psychological, economic, or social harm) than was previously known or recognized.

7.3.2 UNANTICIPATED PROBLEM REPORTING

The investigator will report unanticipated problems (UPs) to the reviewing Institutional Review Board (IRB). The UP report will include the following information:

- Protocol identifying information: protocol title and number, Pl's name, and the IRB project number:
- A detailed description of the event, incident, experience, or outcome;
- An explanation of the basis for determining that the event, incident, experience, or outcome represents an UP;
- A description of any changes to the protocol or other corrective actions that have been taken or are proposed in response to the UP.

To satisfy the requirement for prompt reporting, UPs will be reported using the following timeline:

- UPs that are serious adverse events (SAEs) will be reported to the IRB within 10 working days of the investigator becoming aware of the event.
- Any other UP will be reported to the IRB within 10 working days of the investigator becoming aware of the problem.

8 STATISTICAL CONSIDERATIONS

8.1 STATISTICAL HYPOTHESES

Primary Efficacy Endpoint(s):

The main outcome is minutes per week of moderate- to vigorous-intensity physical activity. The 7-day PAR interview is administered by trained research staff, who will contact participants by telephone and ask about the amount, intensity, and types of physical activities over the past 7 days. The 7-day PAR has demonstrated reliability, congruent validity, and internal consistency. The instrument is sensitive to moderate changes in physical activity over time and has been validated by telephone. Moreover, these self-reported data will provide useful insights regarding the specific types of physical activities occurring in rural counties.

ActiGraph GT3X accelerometers are worn continuously for 7 days during waking (on the nondominant hip) and sleeping (on the nondominant wrist) hours at baseline and at 6, 12, and 18 months. This device measures movement, intensity of physical activity, and sleep efficiency, latency, and number of awakenings. The devices have been validated using heart rate telemetry and total energy expenditure and have been shown to provide valid estimates of sleep. A minimum threshold of 1952 counts per minute will be used for moderate- to vigorous-intensity physical activity with an epoch of 30 seconds. The minimum valid wear time has been set at 4 days of at least 600 minutes of wear. This objectively measured data will be used to corroborate self-reported PAR data

Secondary Efficacy Endpoint(s):

The secondary outcomes include physical performance and anthropometrics. Physical performance is assessed with the Two Minute Step Test, in which participants step in place as fast as possible for 2 minutes while lifting the knees to a premeasured height midway between the upper tips of their patella and iliac crest when standing. A score is calculated based on the number of times the right knee meets the marked height, which can be used to estimate the current level of physical function and predict future physical independence. Anthropometric measurements include height, weight, and waist circumference. Height will be measured without shoes and with a portable stadiometer (Seca 213). Weight will be measured without shoes and in light clothing with a digital scale (Healthometer, model no: 349KLX) that is zeroed before each measurement. Waist circumference will be measured with a Gulick II tension-controlled tape measure (County Technology, Gary Mills). The tape is positioned around the natural waist, just above the iliac crest. The measurement is recorded to the nearest 0.1 cm upon exhalation.

Psychosocial factors will also be assessed at baseline and at 6, 12, and 18 months using Patient-Reported Outcome Measurement Information System scales for anxiety, depression, fatigue, and sleep disturbance with previously demonstrated validity and reliability (α =.95, .98, .84, and .83, respectively).

SCT measures will be assessed in person at the 4 assessment visits and by mail at 3 months (for mediation analyses). The measures include the 10-item self-regulation scale (α =.78), 13-item social support for exercise scale (α =.61-.91), 9-item outcome expectations scale (α =.89), 18-item physical

activity enjoyment scale with high internal consistency and test-retest reliability, 10-item walking self-efficacy scale (α =.82), and the 12-item exercise confidence scale (α =.92).

Secondary measures at baseline, 6 months, and 12 months were included in the cost-effectiveness analyses. We will use a health care utilization survey that captures information on physician and emergency room visits and hospitalizations; the EuroQol-5 Dimension, which estimates utility weights to estimate quality-adjusted life years (QALYs); and a set of questions to measure time spent and expenses related to participation and time devoted to physical activity.

An 18-item measure adapted from similar past studies will assess participant satisfaction with the DIAL intervention and request suggestions for program improvement at 12 and 18 months. Finally, a similar survey will be administered at 18 months to the rural county coordinators to examine stakeholders' perspectives on acceptability, barriers to and facilitators of implementation, and sustainability of the DIAL intervention in the Deep South.

The research staff will complete the three components of the Rural Active Living Assessment (RALA) for each county at baseline. This assessment consists of the street segment assessment to evaluate factors such as walkability, safety features, and terrain of individual, specific street segments; the town-wide assessment that examines community characteristics such as population, total area, and the presence of recreation activities; and finally, the program and policy assessment, which identifies community programs and policies that support physical activity. These tools have been successfully used in similar past studies conducted by our research team in the Deep South.

8.2 SAMPLE SIZE DETERMINATION

Results from our previous UAB pilot study indicated an increase in minutes of moderate-to-vigorous physical activity among the DIAL intervention group compared with the control group. The SD of this measure was 90 minutes. Assuming a mean difference of 35 (SD 90) minutes in moderate-to-vigorous physical activity between the two groups from baseline to 6 months, a two-tailed two-group t test, and a significance level of 5%, we will have 80% power to detect this difference (with an effect size of 0.388) with 105 participants per arm (210 for the study). Assuming a mean change of 35 (SD 90) minutes in moderate-to-vigorous physical activity from baseline to 6 months for the intervention group, a two-tailed paired t test, and a significance level of 5%, we will have 80% power to detect this within-group change (with an effect size of 0.276) with 105 participants. Allowing for 15% attrition, we will recruit 240 participants (120 per arm).

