8.3.2 ANALYSIS OF THE PRIMARY EFFICACY ENDPOINT(S)

The primary method of analysis for physical activity, anthropometrics, and psychosocial measures, all of which will be measured at baseline, 6 months, 12 months, and 18 months, will be mixed model repeated measures analyses. Other general linear mixed model techniques may also be used. These analyses will allow us to examine changes from baseline to follow-up (within-group changes) and differences between the study groups simultaneously, while also accounting for the group-by-time interaction as well as any covariates and interactions that are of scientific interest. An appropriate covariance matrix (eg, autoregressive or unstructured) will be selected based on the final data. The Tukey-Kramer multiple comparisons test will be used to determine specific pairwise differences for statistically significant main effects. Some of these models will include the stratification variable of county and confounding variables (as covariates) such as the baseline BMI category, age, gender, and education level. Some of the models that include physical activity as the dependent variable will be adjusted for wear time. Study variables that will be analyzed using these techniques include the change in minutes of moderate-to-vigorous physical activity. Pearson correlation analysis will be performed to assess the relationship between self-reported and measured physical activity.

Distributions of the aforementioned continuous variables will be examined for normality using box plots, normal probability plots, and the Kolmogorov-Smirnov test. Variables that are determined to deviate from a normal distribution will be log-transformed before statistical testing. Nonparametric tests (eg, the Wilcoxon rank-sum test and the Wilcoxon signed-rank test) may also be used to analyze nonnormally distributed data.

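### Section 8.2: the paired effect size of 0.276 does not match its stated 35 (SD 90), and 240 recruits leave 204 completers at 15% attrition, not the 210 required

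*Combined protocol and SAP*

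**What the plan says.** Section 8.2 (Sample Size Determination) contains two power calculations and an attrition allowance.

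- **Source of the SD.** The pilot is cited with the sentence "The SD of this measure was 90 minutes". The section does not say whether this is the SD of a change or of a single measurement, and it gives no within-person correlation.
- **Two-group test.** The input is "Assuming a mean difference of 35 (SD 90) minutes in moderate-to-vigorous physical activity between the two groups from baseline to 6 months", tested with "a two-tailed two-group t test, and a significance level of 5" percent. The result is "we will have 80% power to detect this difference (with an effect size of 0.388) with 105 participants per arm (210 for the study").
- **Paired test.** The input is "Assuming a mean change of 35 (SD 90) minutes in moderate-to-vigorous physical activity from baseline to 6 months for the intervention group", again two-sided at 5%. The result is "we will have 80% power to detect this within-group change (with an effect size of 0.276) with 105 participants".
- **Attrition.** "Allowing for 15% attrition, we will recruit 240 participants (120 per arm"). The inflation formula is not shown.

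Section 8.3.2 describes the planned analysis as a repeated-measures mixed model and adds: "Study variables that will be analyzed using these techniques include the change in minutes of moderate-to-vigorous physical activity".

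**The concern.** The same mean and SD, 35 and 90, appear in both power sentences, yet one carries an effect size of 0.388 and the other 0.276. If 90 is the SD of the change, the standardised effect is 35/90 in both cases. The tests should then differ in power at a given n, not in effect size.

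The attrition step also does not close. The power statement needs 210 completers, and 240 recruits with 15% loss do not supply them.

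This paragraph is the plan's only justification for enrolling 240, so a reader should be able to reproduce each figure from the inputs beside it. At the plan's own attrition rate, the stated 80% power for the main comparison is also slightly too high.

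**Working it through.** **Inputs, all from section 8.2:** mean difference or change 35 minutes; SD 90; two-sided alpha 0.05; target power 80%; 105 per arm; attrition 15%; 240 recruited in equal arms. Power is from the noncentral t distribution.

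**1. Two-group calculation (reproduces).** d = 35/90 = 0.3889. The noncentrality is d × √(n/2) with 2(n − 1) degrees of freedom.
- At n = 105 per arm: 0.3889 × √52.5 = 2.82, and power is 80.1%.
- The n for 80% power is 104.8, so 105 per arm, as printed.
- The effect detectable with 80% power at 105 per arm is 0.3885, or 35.0 minutes at SD 90. The printed 0.388 fits this.

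**2. Paired calculation (does not reproduce).** d = mean change / SD of change = 35/90 = 0.389. The noncentrality is d × √n with n − 1 degrees of freedom.
- At n = 105: 0.3889 × √105 = 3.99, and power is 97.7%, not 80%. About 54 participants would give 80%.
- Working back from the printed effect size: 0.276 × √105 = 2.83, and power is 80.0%. The effect detectable with 80% power at n = 105 is 0.2760.
- So 0.276, 105 and 80% agree with one another, but they describe a change of 0.276 × 90 = 24.8 minutes. For 35 minutes, they would need an SD of change of 35/0.276 = 126.8.

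**3. Attrition.**
- Completers from 240 at 15% loss: 240 × 0.85 = 204, or 102 per arm.
- Attrition that 240 can absorb: 1 − 210/240 = 12.5%.
- Recruits needed to keep 210: 105/0.85 = 123.5, so 124 per arm and 248 in total.
- Multiplying instead of dividing gives 210 × 1.15 = 241.5, close to 240. This may be where the figure came from.

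**4. Effect of the shortfall.**

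| | 105 per arm | 102 per arm |
|---|---|---|
| Two-group power at 35 (SD 90) | 80.1% | 78.9% |
| Two-group detectable difference, 80% power | 35.0 min | 35.5 min |
| Paired power at 35 (SD 90) | 97.7% | 97.3% |
| Paired detectable change, 80% power | 24.8 min (d = 0.276) | 25.2 min (d = 0.280) |

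**5. Alternative reading of the SD.** Suppose 90 is a single-occasion SD and the two occasions are uncorrelated. The SD of change is then 90 × √2 = 127.3, and the paired effect is 35/127.3 = 0.275, with 79.7% power at n = 105. On that reading, a two-group t test on raw change at 105 per arm has noncentrality 0.275 × √52.5 = 1.99 and only about 51% power.

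**The case against.** There are four points on the other side.

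- **The value 0.276 was not miscalculated.** It is the correct detectable paired effect for 105 participants, and 0.388 appears to be printed on the same convention. This is right, and it identifies the error: a detectable effect stands next to a 35-minute change that it does not describe. The sentence still claims 80% power for that 35-minute change, which is wrong on its own inputs.
- **The 90 might be a single-occasion SD.** With zero correlation this gives 0.275 and 79.7%, close to the printed figures. But it contradicts the sentence's own pairing of a mean change with SD 90, matches less exactly than the detectable-effect reading, and would undermine the two-group calculation. It does not rescue the text. It does make the 0.389 and 97.7% conditional on 90 being the SD of change.
- **The origin of 240 can be guessed, and the plan never says that 240 less 15% leaves 210.** Both are true. The shortfall is inferred from the three printed numbers, and the multiplication shortcut still does not preserve 210 completers.
- **The consequence is negligible.** Three completers per arm matter less than the uncertainty in an SD taken from a 63-participant pilot (section 2.2). The mixed model can also use participants with partial follow-up, so a completer count is only approximate. This stands, and it is why the point is minor.

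**Conclusion.** The concern holds, as a minor one. On its literal inputs, the paired sentence should give an effect size of 0.389 and 97.7% power; it prints 0.276 and 80%. At 15% attrition, 240 recruits yield 204 completers, six short of the 210 required, and two-group power is 78.9% instead of 80.1%.

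The two-group requirement of 105 per arm, which sets the trial size, is unaffected. The paired error understates power, so it does not threaten the sample size.

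These conclusions take 90 as the SD of the 6-month change, which is how both power sentences read, and use completer t tests as the plan does. If 90 is instead a single-occasion SD, both power calculations need redoing. The 51% above is the zero-correlation case for raw change, and a baseline-adjusted model would do better.

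**What to change.** Reword section 8.2, with no added enrolment and no change to the analysis.

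1. State whether 90 is the SD of the 6-month change, since section 8.3.2 analyses change in minutes. If it is, 105 per arm stands and steps 2 and 3 apply as written. If not, give the SD of change and derive both calculations from it.
2. In the paired sentence, either give an effect size of 0.389 with 97.7% power at n = 105, or keep 0.276 and label it the smallest paired effect detectable with 80% power (24.8 minutes at SD 90).
3. For attrition, either state 12.5%, or keep 15% and state 204 completers (102 per arm) with about 79% two-group power. In the second case, the paired figures at n = 102 are 97.3% power, or a detectable change of 25.2 minutes (d = 0.280).

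The cost is one rewritten paragraph. If 15% is kept, the stated two-group power falls from 80% to about 79%.
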